10.2 Sample size

Figure 1 shows the sample size determination for a paired t-test, ($\alpha=0.05$), in order to detect a difference in mean subjective handling scores between lenses. Assuming a standard deviation of 1.2, a sample size of about 33 completed subjects provides 90% power to detect a difference in subjective handling ratings of 0.7 points on a 0 - 10 scale. In order to account for potential subject dropouts or AEs, 10%-15% should be added to the sample size. Therefore, 38 subjects should be enrolled with the aim to complete 33.

11 Data Quality Assurance

11.1 Study monitoring

A site visit or discussion may be conducted during the course of the study as appropriate. Prior to final data freeze, a close-out visit/discussion may be warranted to check for accuracy and completeness of records. The sponsor or sponsor's representatives will be authorized to gain access to the source documentation for the purposes of monitoring and auditing the study.

11.2 Record keeping

Detailed records of all study visits will be made using the electronic Case Report Forms (CRFs).

11.3 Record retention

Following study completion, data will be available in electronic and/or paper format for audit, sponsor use, or subsequent analysis. The original clinical raw data (including completed CRFs and Informed Consent forms) will be retained according to guidelines set forth in the general work agreement with the site. The Sponsor will be notified and consulted if ever the files are to be destroyed. In the event that this implementation document is indicated for design verification and validation purposes, as indicated on the title page, all original raw data forms and completed CRF's will be forwarded to the sponsor at completion of the final report.

11.4 Data Entry / Data Management

Data will be entered into an electronic spreadsheet. Study staff will only be able to modify the data file via password entry. The investigators will be responsible for the data integrity, and complete data entry for each visit as well as the take home questionnaires. The investigator will send the data collected to the study sponsor within 5 business days after the last subject completes the final visit.

11.6 Publication

The investigators will not be permitted to publish or present at scientific meetings results obtained from the clinical study without prior written consent from the sponsor.

[REDACTED]

[REDACTED]

[REDACTED]

[REDACTED]

[Redacted]

[Redacted]

[Redacted]

[Redacted]

[Redacted]

[Redacted]

[Redacted]

APPENDIX 1 – STATEMENT OF INFORMED CONSENT

APPENDIX 2- STUDY TIMELINE *

TASK	Aug-2021	Sept-2021	Oct-2021	Nov-2021	Dec-2021	Jan-2022
Generate study Protocol.	Aug 16 - 19					
Protocol EC submission.	Aug 19-20					
Protocol EC approval.	Sept 20 th					
First Subject First Visit (FSFV).		Week of Sept 20 th				
Last Subject Last Visit (LSLV).				Week of Nov 30 th		
Study report.					Dec 15 th .	

**This timeline is subject to change depending on COVID-19 situation, participant enrollment, lens power availability, and study progress.*

APPENDIX 3-LENS RANDOMIZATION

APPENDIX 4 – LENS REPLACEMENT LOG

Date	Investigator Initials	Subject Initials	Visit Just Prior to Lens Replacement	Number of Days Lens was Worn prior to Replacement	Lens Replaced (check one)	Reason
Click here to enter a date.					 Right  Left  Both	
Click here to enter a date.					 Right  Left  Both	
Click here to enter a date.					 Right  Left  Both	
Click here to enter a date.					 Right  Left  Both	
Click here to enter a date.					 Right  Left  Both	
Click here to enter a date.					 Right  Left  Both	
Click here to enter a date.					 Right  Left  Both	
Click here to enter a date.					 Right  Left  Both	
Click here to enter a date.					 Right  Left  Both	
Click here to enter a date.					 Right  Left  Both	
Click here to enter a date.					 Right  Left  Both	
Click here to enter a date.					 Right  Left  Both	
Click here to enter a date.					 Right  Left  Both	
Click here to enter a date.					 Right  Left  Both	

APPENDIX 5 – GRADING SCALES
GRADING & MEASUREMENT SYSTEM

Variable	Assessment Method	Grading/Measurement System
Wearing Times		
Average # of days lenses worn in a week	Enter the number of days lenses are worn during the week.	Days per week
Average Daily Wearing Time	Typical time of day when lenses inserted and removed.	Time of day to nearest half hour
Average # of hours of wear per day	Enter the number of hours lenses are worn per day.	Hours per day
Average Comfortable Wearing Time	Typical time of day when subject first experiences lens awareness or irritation.	‘Does CL comfort deteriorate during wear?’ (tick-box). If yes, record time of day to nearest half hour when first aware of lenses
Typical Removal Time	Typical time of day when subject removes the lens.	Time of day to nearest half hour
Subjective Assessments (Questions asked by the investigator and recorded)		
Comfort, dryness, handling, lens fit, vision satisfaction.	Assessed by subject on a 0-10 scale.	0-10 scale Comfort: (10= can’t feel) Dryness: (10=no dryness) Handling: (10=very easy) Fit stability (10=very stable) * Vision: (10=very satisfied)
Vision Quality	Assessed by subject on a 0-10 scale.	Vision quality: (10=Excellent vision, totally sharp)
Night Vision Quality	Assessed by subject on a 0-10 scale.	Vision quality: (10=Excellent vision, totally sharp)
Vision Stability	Assessed by subject on a 0-10 scale.	Vision stability: (10=perfectly stable, not fluctuating, changing)
Satisfaction	Subject’s assessment of various symptoms on a 4-point Likert scale.	1. Completely satisfied 2. Somewhat satisfied 3. Somewhat dissatisfied 4. Completely dissatisfied
Preference	Subject’s preference for one of two contact lenses.	Forced choice: Study lenses or Habitual
Vision		
Distance VA – High contrast	Measured using Snellen or logMAR chart.	Snellen or logMAR visual acuity (VA) to nearest letter.

Variable	Assessment Method	Grading/Measurement System
Lens Surface assessed using slit lamp		
Front Surface Wettability	Lens surface viewed with a slit lamp, white diffuse light and broad beam under low-medium magnification.	0 – 4 0=poor 4=excellent
Lens surface deposits assessed using the slit-lamp		
Front Surface Deposits	Lens surface deposits viewed with a slit lamp, white diffuse light and broad beam under low-medium magnification.	0 Clean, no deposits 1 5 or less small deposits (<0.1 mm) 2 > 5 deposits of <0.1 mm size or film covering 25-50% of surface 3 Deposits of between 0.1 and 0.5 mm or film covering 50-75% of surface 4 Deposits of 0.5 mm or larger or film covering more than 75% of surface
Lens Fit- assessed using slit lamp		
Lens Centration	Lens centration will be recorded by degree and direction in the primary position.	0 Centered - optimal 1 Decentered slightly 2 Substantially decentered (≥ 0.5 mm) If decentered, direction(s) will be recorded as: Superior, Inferior, Nasal, Temporal
Corneal Coverage	Assessed in primary gaze.	Y Yes, full corneal coverage at all times N No, incomplete corneal coverage
Post-Blink Movement	Assessed immediately after the blink - lower lid to be depressed only if necessary, for observation.	0 Insufficient, unacceptable movement 1 Minimal, but acceptable movement 2 Optimal movement 3 Moderate, but acceptable movement 4 Excessive, unacceptable movement
Lens orientation in primary position of gaze	Slit lamp, with 10x magnification. Nasal mislocation is recorded as (+) and temporal as (-)	Mislocation of the axis mark on the lens relative to the 6 o'clock position, zero rotation, measured in degrees.
Overall stability	Slit lamp, with 10x magnification.	(0–4 scale), where 0=very poor, 4= excellent
Rotational recovery in degrees after 60 seconds	Slit lamp, with 10x magnification.	Lens ability to return to its original position measured 60 seconds after manually rotating the lens 45° degrees temporally. Rotational recovery (RR) is assessed by manually rotating the lens 45° temporally from the primary gaze orientation (PGO) and allowing one minute (60 seconds) for the lens to recover. The absolute difference between the position of the lens following the recovery period and the PGO is taken as the measure of interest.

Variable	Assessment Method	Grading/Measurement System
Overall Fit Acceptance	Assessed by the Investigator based on lens fit alone (i.e., not comfort or vision).	0 Should not be worn 1 Borderline but unacceptable 2 Min. acceptable, early review 3 Not perfect but OK to dispense 4 Perfect
Biomicroscopy		
Limbal & Bulbar Hyperemia	Assessed using slit lamp with white light, low-medium magnification. (Use Brien Holden Vision Institute grading scales for reference) ½ grades recorded.	0 NONE: No injection present 1 VERY SLIGHT 2 SLIGHT 3 MODERATE 4 SEVERE
Lower palpebral hyperemia	Assessed using slit lamp with white light, low-medium magnification. (Use Brien Holden Vision Institute grading scales for reference) ½ grades recorded.	0 NONE: No injection present 1 VERY SLIGHT 2 SLIGHT 3 MODERATE 4 SEVERE
Corneal Infiltrates	Assessed using slit lamp with diffuse white light, low-medium magnification.	0 NONE: No infiltrates 1 TRACE: One faint peripheral infiltrate that does not stain. 2 MILD: A few mild infiltrates 3 MODERATE: Multiple dense infiltrates 4 SEVERE: Marked infiltrates with overlying staining.
Other Slit Lamp Findings	This section is intended to capture less commonly observed clinical entities such as conjunctival infection, EKC, corneal ulcers, lens adhesions, and recurrent erosions. The complication should be identified, described and graded by severity using the 0-4 scale.	0 None 1 Trace 2 Mild 3 Moderate 4 Severe

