10.1 Statistical analysis

Summary statistics will be produced (e.g., mean, standard deviation). Differences between lenses will be compared using Paired t-tests. Paired t-tests /analysis of variance for normal (interval/continuous) data, Wilcoxon's signed ranks test for non-normal (ordinal) data, chi-squares test for nominal data. A Binomial test will be used to evaluate lens preference questions. All participants who were evaluated will be used in the analysis. In the event of missing data, individual data points will be excluded in the analysis and not extrapolated from the collected data.

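### Post-blink movement is best at the middle of its scale, so a Section 10.1 test on the raw grade shows which lens moves more, not which is closer to optimal; signed orientation has the same problem if zero rotation is the optimum.

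*Combined protocol and SAP*

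**What the plan says.** Appendix 5, under Lens Fit, grades post-blink movement as "0 Insufficient, unacceptable movement 1 Minimal, but acceptable movement 2 Optimal movement 3 Moderate, but acceptable movement 4 Excessive, unacceptable movement".

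The same table records orientation in primary gaze with a sign: "Nasal mislocation is recorded as (+) and temporal as" negative. The reference is the 6 o'clock "position, zero rotation, measured in degrees". The table calls the deviation a mislocation but does not say that zero is the best value.

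Two neighbouring rows already separate size from direction. For centration, "Lens centration will be recorded by degree and direction in the primary position". For rotational recovery, "The absolute difference between the position of the lens following the recovery period and the PGO is taken as the measure of interest".

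Section 10.1 allocates tests by type of data. "Differences between lenses will be compared using Paired t-tests" is the general rule, with Wilcoxon's "signed ranks test for non-normal (ordinal) data, chi-squares test for nominal data". It also says "Summary statistics will be produced (e.g., mean, standard deviation"). It has no rule specific to movement or orientation, and no visible redaction that might hide one.

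**The concern.** A Wilcoxon or paired t-test on recorded values asks whether one lens tends to score higher than the other. That answers a quality question only when higher is consistently better or consistently worse. For movement it is neither.

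Two misreadings follow. A lens whose fits are too tight in some subjects and too loose in others can look the same as a lens that is nearly always optimal. And two lenses equally far from optimal, one tending tight and one tending loose, can produce a small p-value although neither fits better. What is at stake is that a movement or orientation p-value might be reported as evidence on fit quality.

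**Working it through.** **The plan's own figure.** Section 10.2 gives 33 completers for 90% power to detect 0.7 points in handling with SD 1.2 and α = 0.05. Reading 1.2 as the SD of paired differences, the noncentrality is (0.7/1.2)·√33 = 3.35. The exact two-sided paired t-test then has power 90.1% at 33 and 89.2% at 32, so the figure reproduces. It concerns handling only and is not in question here. It supplies n = 33 below.

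**Method.** Every distribution below is my assumption. Each run uses 33 subjects, one value per subject and lens, a two-sided 5% level, and lenses independent within subject unless stated. Movement was tested by Wilcoxon signed-rank (zeros dropped, tie-corrected normal approximation) on the raw grade and on the folded grade |grade − 2|. Orientation was tested by paired t-test on signed and on absolute degrees. Simulation error is at most about 1 percentage point.

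**Movement, acceptable grades only (1/2/3).**

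For 10/80/10 v 20/60/20 the expected raw grades are 0.10·1 + 0.80·2 + 0.10·3 = 2.0 and 0.20·1 + 0.60·2 + 0.20·3 = 2.0, which are identical. The expected folded grades are 0.10 + 0.10 = 0.2 and 0.20 + 0.20 = 0.4. For the mirror-image pair 25/65/10 v 10/65/25 the raw means are 1.85 and 2.15, while both folded means are 0.35.

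| Lens A v lens B, % at grades 1/2/3 | Raw | Folded |
|---|---|---|
| 10/80/10 v 15/70/15 | 5% | 13–14% |
| 10/80/10 v 20/60/20 | 5% | 41% |
| 25/65/10 v 10/65/25 (equally good) | 54% | 5% |
| 15/75/10 v 10/75/15 (equally good, milder) | 12% | 4% |
| 10/80/10 v 5/60/35 (faults mostly one way) | 64% | 41% |

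Rows 1 and 2 are real quality differences that the raw test finds no more often than chance. Rows 3 and 4 are not quality differences, yet the raw test reports them too often. Row 5 is a real quality difference where the raw test does better.

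**Orientation, if zero is the optimum.**

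| Contrast, degrees | Signed | Absolute |
|---|---|---|
| Both centred at 0, SD 5 v 6 | 5% | 15% |
| Both centred at 0, SD 5 v 7.5 | 5% | 53–54% |
| Centre 0 v 3, both SD 5 | 65–66% | 13% |
| Same, between-lens correlation 0.5 | 92% | 15% |
| Centre 0 v 5, both SD 5 | 98% | 54% |

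The absolute value picks up wider spread that the signed test cannot see. The signed test is much better at finding a pure shift.

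**The case against.** The strongest reply is that nothing visible says these two items will be tested between lenses. The outcomes listed after handling and most of the visit measurements are redacted, and Appendix 5 is a measurement guide, not an analysis list. A reader might infer that the trial will draw wrong conclusions about fit. The documents do not support that, and the point has to be conditional on such a comparison being made.

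The raw tests are also valid for their own questions: which lens moves more, and whether there is nasal or temporal bias. Fit quality is covered by measures that run in one direction: overall fit acceptance, overall stability and rotational recovery. The planned standard deviation would show a wider orientation spread, though without a test. All of this stands and keeps the point minor.

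Folding has its own assumptions and costs. |grade − 2| treats minimal and moderate movement as equally far from optimal, and likewise insufficient and excessive; the documents pair them as acceptable or unacceptable but never call them equal. Folding loses power when faults go one way, as the tables show. So the inference that the folded result should replace the raw one does not hold.

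For orientation, zero as the optimum is an inference from the wording. The rotational-recovery precedent is measured from the lens's own primary-gaze position, not from zero rotation. It supports separating size from direction, but not zero as the reference.

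Finally, because lenses are worn in both eyes, a reader might infer that nasal and temporal values will cancel when the eyes are averaged. No visible text plans averaging. Under nasal/temporal coding, mirror-symmetric eyes have the same sign, so systematic cancellation would need one eye nasal and the other temporal, which the documents give no reason to expect. It is a reason to fold per eye, not evidence of a fault.

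**Conclusion.** The point holds at the lowest level of importance: firmly for post-blink movement, whose mid-scale optimum is explicit, and conditionally for orientation. Followed as written, Section 10.1 would compare amount or direction rather than closeness to the optimum.

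The size depends on unknown distributions. With evenly split faults at 80% v 60% optimal, folding raises detection from about 5% to 41%; at 80% v 70% it reaches only 13–14%. False signals from mirror-image lenses range from about 12% to 54% in the two cases tried. Larger contrasts would give more dramatic figures, but Visit 1b discontinues subjects whose lenses are unsuitable to dispense, which limits how many unacceptable grades to expect.

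The handling outcome, the sample size and safety are unaffected.

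**What to change.** Add to Section 10.1: *For any between-lens comparison of fit quality, post-blink movement is also compared as |grade − 2|, and orientation as absolute degrees from the intended reference (zero rotation unless stated otherwise), computed for each eye before any combination of eyes. Raw-grade and signed comparisons are reported alongside, labelled as comparisons of amount and direction, with grade frequencies by lens.*

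If zero rotation is not the intended reference for orientation, name the reference and fold about that value.

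The cost is two sentences and one extra analysis per item, on data the grading system already defines. The drawbacks are the equal-distance assumption in |grade − 2| and the lower power of the folded test for one-way faults or shifts, which is why both results should be kept. Settling this before unmasking also prevents a choice between signed and absolute results once they are known.

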APPENDIX 6– CRF's / UNSCHEDULED VISIT & ADVERSE EVENT FORM
